5.7.8 Additional Research Collection

This protocol will include residual sample storage for additional research (AR).

For All US sites:

Additional research participation is required for all investigational sites in the US.

For non-US Sites:

Additional research is optional for all study participants, except where retention and/or collection is prohibited by local laws or regulations, ethics committees, or institutional requirements.

This collection for additional research is intended to expand the translational R&D capability at BMS, and will support as yet undefined research aims that will advance our understanding of disease and options for treatment. It may also be used to support health authority requests for analysis, and advancement of pharmacodiagnostic development to better target drugs to the right patients. This may also include genetic/genomic exploration aimed at exploring disease pathways, progression and response to treatment etc.

Sample Collection and Storage

All requests for access to samples or data for additional research will be vetted through a diverse committee of the study sponsor's senior leaders in Research and Development (or designee) to ensure the research supports appropriate and well-defined scientific research activities.

- Residual samples from tumor biopsies and biomarker collections Table 5.7.8-1 will also be retained for additional research purposes.

Samples kept for future research will be stored at the BMS Biorepository in [REDACTED] USA or an independent, BMS-approved storage vendor.

The manager of these samples will ensure they are properly used throughout their usable life and will destroy the samples at the end of the scheduled storage period, no longer than fifteen (15) years after the end of the study or the maximum allowed by applicable law.

Transfers of samples by research sponsor to third parties will be subject to the recipient's agreement to establish similar storage procedures.

Samples will be stored in a coded fashion, and no researcher will have access to the key. The key is securely held by the Investigator at the clinical site, so there is no direct ability for a researcher to connect a sample to a specific individual.

Further details of sample collection and processing will be provided to the site in the procedure manual.

Table 5.7.8-1: Residual Sample Retention for Additional Research Schedule

Sample Type	Time points for which residual samples will be retained
Tumor Biopsies	[REDACTED]
Biomarker Blood Collections	
PK Blood Collections	

5.8 Outcomes Research Assessments

Not applicable.

5.9 Other Assessments

5.9.1 Immunogenicity Assessments

Blood samples for immunogenicity analysis of relatlimab and nivolumab will be collected according to the schedule given in [Table 5.5.1-1](#) and [Table 5.5.1-2](#). These samples will be evaluated for the development of anti-drug antibody (ADA) for relatlimab and nivolumab by validated immunoassays. Additional characterization (eg, neutralizing antibody (NAB) assay) for any detected ADA may also be performed using a validated assay. On-treatment samples are intended to be drawn relative to actual dosing days. If a dose occurs on a different day within the cycle, immunogenicity samples should be adjusted accordingly.

Selected serum samples may be analyzed by an exploratory orthogonal method that measures anti-relatlimab or anti-nivolumab. Potential results generated from any orthogonal method are intended as informational for technology exploration purposes and will not be reported.

Selected immunogenicity samples also may be analyzed for exploratory analyses; exploratory results will not be reported.

In addition, ad hoc serum samples designated for PK or biomarker assessments may also be used for immunogenicity analysis if required (eg, insufficient volume for complete immunogenicity assessment or to follow up on suspected immunogenicity related AE).

5.10 Results of Central Assessments

The effect of relatlimab on QTc interval when administered as monotherapy or in combination with nivolumab will be evaluated by a central reader using ECG data collected via Holter monitors supplied by a core laboratory; these results will be summarized at the end of the study. For the purposes of monitoring subject safety, Investigators will review 12-lead ECGs per the protocol-specified schedule (see [Table 5.1-2](#)) using their site's standard electrocardiogram machines.

6 ADVERSE EVENTS

An *Adverse Event (AE)* is defined as any new untoward medical occurrence or worsening of a preexisting medical condition in a clinical investigation subject administered an investigational (medicinal) product and that does not necessarily have a causal relationship with this treatment. An AE can therefore be any unfavorable and unintended sign (such as an abnormal laboratory finding), symptom, or disease temporally associated with the use of investigational product, whether or not considered related to the investigational product.

The causal relationship to study drug is determined by a physician and should be used to assess all adverse events (AE). The causal relationship can be one of the following:

- Related: There is a reasonable causal relationship between study drug administration and the AE.
- Not related: There is not a reasonable causal relationship between study drug administration and the AE.

The term "reasonable causal relationship" means there is evidence to suggest a causal relationship.

Adverse events can be spontaneously reported or elicited during open-ended questioning, examination, or evaluation of a subject. Care should be taken not to introduce bias when collecting AE and/or SAEs. Inquiry about specific AEs should be guided by clinical judgement in the context of known adverse events, when appropriate for the program or protocol.

6.1 Serious Adverse Events

A *Serious Adverse Event (SAE)* is any untoward medical occurrence that at any dose:

- results in death.
- is life-threatening (defined as an event in which the subject was at risk of death at the time of the event; it does not refer to an event which hypothetically might have caused death if it were more severe).
- requires inpatient hospitalization or causes prolongation of existing hospitalization (see **NOTE** below).
- results in persistent or significant disability/incapacity.
- is a congenital anomaly/birth defect.
- is an important medical event (defined as a medical event(s) that may not be immediately life-threatening or result in death or hospitalization but, based upon appropriate medical and scientific judgment, may jeopardize the subject or may require intervention [eg, medical, surgical] to prevent one of the other serious outcomes listed in the definition above.) Examples of such events include, but are not limited to, intensive treatment in an emergency room or at home for allergic bronchospasm; blood dyscrasias or convulsions that do not result in hospitalization.) Potential drug induced liver injury (DILI) is also considered an important medical event. (See [Section 6.6](#) for the definition of potential DILI.).

Suspected transmission of an infectious agent (eg, pathogenic or nonpathogenic) via the study drug is an SAE.

Although pregnancy, overdose, cancer, and potential drug induced liver injury (DILI) are not always serious by regulatory definition, these events must be handled as SAEs. (See Section 6.1.1 for reporting pregnancies).

NOTE:

The following hospitalizations are not considered SAEs in BMS clinical studies:

- a visit to the emergency room or other hospital department < 24 hours, that does not result in admission (unless considered an important medical or life-threatening event).
- elective surgery, planned prior to signing consent.
- admissions as per protocol for a planned medical/surgical procedure.
- routine health assessment requiring admission for baseline/trending of health status (eg, routine colonoscopy).
- medical/surgical admission other than to remedy ill health and planned prior to entry into the study. Appropriate documentation is required in these cases.
- admission encountered for another life circumstance that carries no bearing on health status and requires no medical/surgical intervention (eg, lack of housing, economic inadequacy, caregiver respite, family circumstances, administrative reason).

6.1.1 *Serious Adverse Event Collection and Reporting*

Following the subject's written consent to participate in the study, all SAEs, whether related or not related to study drug, must be collected, including those thought to be associated with protocol-specified procedures. All SAEs must be collected that occur during the screening period and within 135 days of discontinuation of dosing or until starting a new anti-neoplastic treatment (whichever occurs first). If applicable, SAEs must be collected that relate to any later protocol-specified procedure (eg, a follow-up skin biopsy).

All SAEs that occur during the screening period and within 100 days after discontinuation of dosing must be collected except in cases where a study participant has started a new anti-neoplastic treatment.

However, any SAE occurring after the start of a new anti-neoplastic treatment that is suspected to be related to study treatment by the investigator should be reported as an SAE.

The investigator should report any SAE that occurs after these time periods and that is believed to be related to study drug or protocol-specified procedure.

An SAE report should be completed for any event where doubt exists regarding its seriousness.

If the investigator believes that an SAE is not related to study drug, but is potentially related to the conditions of the study (such as withdrawal of previous therapy or a complication of a study procedure), the relationship should be specified in the narrative section of the SAE Report Form.

SAEs, whether related or not related to study drug, and pregnancies must be reported to BMS (or designee) within 24 hours. SAEs must be recorded on the SAE Report Form; pregnancies on a Pregnancy Surveillance Form (electronic or paper forms). When using paper forms, the reports are to be transmitted via email or confirmed facsimile (fax) transmission to:

SAE Email Address: Refer to Contact Information list.

SAE Facsimile Number: Refer to Contact Information list.

For studies capturing SAEs through electronic data capture (EDC), electronic submission is the required method for reporting. The paper forms should be used and submitted immediately, only in the event the electronic system is unavailable for transmission. When paper forms are used, the original paper forms are to remain on site.

SAE Telephone Contact (required for SAE and pregnancy reporting): Refer to Contact Information list.

If only limited information is initially available, follow-up reports are required. (Note: Follow-up SAE reports should include the same investigator term(s) initially reported.)

If an ongoing SAE changes in its intensity or relationship to study drug or if new information becomes available, a follow-up SAE report should be sent within 24 hours to the BMS (or designee) using the same procedure used for transmitting the initial SAE report.

All SAEs should be followed to resolution or stabilization.

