5.3 Safety Assessments

Adverse events will be assessed continuously during the study and for 135 days after the last treatment. Adverse events will be evaluated according to NCI CTCAE version 4.0 and should be followed per requirements in [Sections 6.1.1](#) and [6.2.1](#). Adverse events will be coded using the most current version of Medical Dictionary for Regulatory Activities (MedDRA) and reviewed for potential significance and importance.

Protocol-specified assessments are described in [Table 5.1-1](#) (Screening Procedural Outline), [Table 5.1-2](#) (On-Treatment Procedural Outline), and [Table 5.1-3](#) (Follow-Up Procedural Outline).

5.3.1 *Imaging Assessment for the Study*

Any incidental findings of potential clinical relevance that are not directly associated with the objectives of the protocol should be evaluated and handled by the Study Investigator as per standard medical/clinical judgment.

5.3.2 *Genomic Analysis*

In order to identify potential polymorphisms associated with safety and efficacy of relatlimab, selected genes will be evaluated for single nucleotide polymorphisms (SNP). Analysis will include but not be limited to sequence polymorphisms linked to genes and pathways associated with [REDACTED] and [REDACTED]

██████████ DNA may also be utilized for DNA sequencing to identify germline sequences to compare with tumor sequences.

5.3.3 **Laboratory Test Assessments**

A central/local laboratory will perform the analyses and will provide reference ranges for these tests.

Clinical laboratories will be assessed at the time points indicated in [Table 5.1-1](#) (Screening Procedural Outline), [Table 5.1-2](#) (On-Treatment Procedural Outline), and [Table 5.1-3](#) (Follow-Up Procedural Outline).

At screening, sites should collect samples during the timeframes indicated in Table 5.1-1 and ensure that results required for eligibility are verified prior to registration. During treatment, unless otherwise indicated in Table 5.1-2, results of clinical laboratory test must be reviewed prior to dosing.

The following clinical laboratory tests will be performed:

Hematology (Local Laboratory)

Complete blood count (CBC) with differential
Platelet count
INR (screening only)

Serum Chemistry (Local Laboratory)

Aspartate aminotransferase (AST)	C-reactive protein
Alanine aminotransferase (ALT)	Albumin
Total bilirubin	Sodium
Alkaline phosphatase	Potassium
Lactate dehydrogenase (LDH)	Chloride
Creatinine	CO ₂
Blood urea nitrogen (BUN)	Calcium

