6.2.1 Non-serious Adverse Event Collection and Reporting

The collection of non-serious AE information should begin at initiation of study drug and for 135 days after discontinuation of dosing or until starting a new anti-neoplastic treatment (whichever occurs first). Non-serious AE information should also be collected from the start of a placebo lead-in period or other observational period intended to establish a baseline status for the subjects.

Non-serious AEs should be followed to resolution or stabilization, or reported as SAEs if they become serious (see [Section 6.1.1](#)). Follow-up is also required for non-serious AEs that cause interruption or discontinuation of study drug and for those present at the end of study treatment as appropriate. All identified non-serious AEs must be recorded and described on the non-serious AE page of the CRF (paper or electronic).

Completion of supplemental CRFs may be requested for AEs and/or laboratory abnormalities that are reported/identified during the course of the study.

Immune-mediated adverse events are AEs consistent with an immune-mediated mechanism or immune-mediated component for which non-inflammatory etiologies (eg, infection or tumor progression) have been ruled out. IMAEs can include events with an alternate etiology which were

exacerbated by the induction of autoimmunity. Information supporting the assessment will be collected on the subject's case report form.

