8.3 Endpoints

8.3.1 Primary Endpoint(s)

The primary endpoint of this Phase 1 study is safety as measured at the study level by the rate of AEs, SAEs, AEs leading to discontinuation, deaths, and laboratory abnormalities, assessed during treatment and for up to 135 days after the last treatment. All subjects who receive at least one dose of relatlimab alone or in combination with nivolumab will be analyzed for safety.

Co-primary endpoint in Part D is objective response rate (ORR) and duration of response (DOR) (see [Section 8.3.2.3](#) for details).

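### Section 6.1.1 sets both a 135-day and a 100-day window for collecting all SAEs, and the shorter one ends before the primary safety endpoint does

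*Combined protocol and SAP*

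**What the plan says.** Section 6.1.1 gives two instructions on collecting SAEs regardless of cause, in consecutive paragraphs of current text:

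- First: "All SAEs must be collected that occur during the screening period and within 135 days of discontinuation of dosing", with an earlier stop if the subject begins new anticancer therapy.
- Second: "All SAEs that occur during the screening period and within 100 days after discontinuation of dosing must be collected", with an exception for subjects who have begun such therapy.

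Two further paragraphs extend reporting. SAEs after the start of new therapy are still reportable if the investigator suspects study treatment. SAEs after the stated periods are reportable if attributed to study drug or a protocol procedure.

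Section 8.3.1 makes the SAE rate, whatever the cause, a component of the primary safety endpoint, alongside the rates of other AEs, deaths and abnormal laboratory results. It gives the window for all of these as "assessed during treatment and for up to 135 days after the last treatment". The Synopsis repeats this. Section 5.3 says: "Adverse events will be assessed continuously during the study and for 135 days after the last treatment". Section 6.2.1 says: "The collection of non-serious AE information should begin at initiation of study drug and for 135 days after discontinuation of dosing", again with an earlier stop at new anticancer therapy. The Clinical Follow-up period in Section 3.1 is also 135 days.

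**The concern.** SAE rate is a named component of the primary endpoint, and Section 8.3.1 does not restrict it to related events. If a site or case report form works to 100 days, routine collection of all SAEs ends 35 days before the endpoint window closes, while non-serious events are still collected to Day 135. From Day 101, whether a new SAE is captured would depend largely on the investigator's causality call. Capture could then differ between sites for a reason unrelated to the drug. The study is open-label, and Section 7 marks a data monitoring committee as not applicable.

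**Working it through.** The plan gives no figure to reproduce here. The check sets the stated windows side by side.

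| Source | Days after last dose or treatment | Stop at new anticancer therapy? |
|---|---|---|
| 6.1.1, first SAE sentence | 135 | Yes |
| 6.1.1, second SAE sentence | 100 | Yes |
| 6.2.1, non-serious AEs | 135 | Yes |
| 5.3, AE assessment | 135 | None stated |
| 8.3.1, primary safety endpoint | 135 | None stated |
| 3.1, Clinical Follow-up | 135 | None stated |

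I take discontinuation of dosing and last treatment as the same day.

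**Step 1: the gap.** 135 − 100 = 35 days (Days 101 to 135). As a share of the post-treatment window, 35/135 = 25.9%. Under the 135-day sentence the gap is 0.

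**Step 2: who is exposed.** For a subject starting new therapy on Day t, both sentences stop at t. The extra loss from the 100-day sentence is max(0, min(t, 135) − 100):

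- t of 100 or less: 0 days
- t = 120 (illustrative): 20 days
- no new therapy by Day 135: 35 days

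So 35 days is a maximum, reached only by subjects still alive, in follow-up and off new therapy at Day 135.

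**Step 3: the gap against the whole endpoint window.** The endpoint also covers treatment, up to twelve 8-week cycles: 12 × 56 = 672 days. If the last treatment is placed at the end of cycle 12, with no delays, the share is 35/(672 + 135) = 35/807 = 4.3%. For a subject who stops after very few doses it approaches 25.9%. These are shares of calendar time, not of events.

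**Step 4: which events are exposed.** Several routes remain open after Day 100 even under the shorter window:

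- SAEs attributed to study drug or a protocol procedure (6.1.1)
- non-serious events that become serious, since those are collected to Day 135 (6.2.1)
- intentional overdose (6.5) and potential drug-induced liver injury (6.6), which must be reported as SAEs

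What remains is mainly new-onset SAEs judged unrelated. Section 8.3.1 still counts those.

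**Step 5: is the 100-day figure supported elsewhere?** No other AE or SAE collection statement uses it. The protocol's other 100-day periods concern live vaccines (3.4.1) and time since autologous transplant (3.3.1).

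**Step 6: what deletion leaves open.** With only the 135-day sentence, a subject starting new therapy on Day t still has 135 − t days of the endpoint window without collection of all SAEs. Sections 5.3 and 8.3.1 state no such cut-off.

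**The case against.** The strongest reply is that the text forces no loss. Both sentences are commands to collect, one window contains the other, and the 100-day sentence never tells sites to stop. Full compliance means Day 135. Nothing in the documents shows a site, form or database using 100 days. The visit-level cells of the follow-up schedule (Table 5.1-3) are blank in the public copy, so the operative instruction cannot be seen. No hypothesis is formally tested and safety is summarised descriptively. On this view it is one stray sentence.

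Much of that stands, and it rules out three stronger readings that a reader might infer:

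- *That about a quarter of late SAEs are lost for every subject.* The 25.9% is a share of post-treatment days, and many subjects may have a smaller gap or none.
- *That late SAEs would arrive only if judged drug-related.* The other routes listed above contradict this.
- *That late deaths go unrecorded.* Section 3.6 requires follow-up for outcome or survival data as applicable, and Section 8.2 uses deaths within 135 days of the last relatlimab dose. Death ascertainment does not rest on 6.1.1 alone, although formal Survival Follow-up covers only Hodgkin lymphoma subjects in Parts C and D.

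The reply does not remove the fault. Two different mandatory windows for one primary-endpoint component leave the choice to the reader, and the later statement is the one that falls short of the endpoint.

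**Conclusion.** The point holds as a contradiction in a data-collection rule for a primary-endpoint component. It is not evidence that events have been lost. The 100-day sentence is the outlier against every other safety window compared here. Where it is applied, up to 35 days per subject fall outside routine collection of all SAEs, and capture of mainly unrelated, new-onset events becomes dependent on causality and on site. The documents give no SAE rates or timing for Days 101 to 135, so the size of any under-count is unknown and could be zero.

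This rests on two assumptions: that discontinuation of dosing and last treatment mark the same day, and that the endpoint counts SAEs whatever their cause, as Section 8.3.1 reads. A reader might also infer that deleting the sentence makes Section 6.1.1 agree with Sections 5.3 and 8.3.1. It does not, because the stop at new anticancer therapy remains.

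**What to change.** 1. Delete the 100-day sentence from Section 6.1.1, leaving one 135-day window for all SAEs regardless of cause. The provision on related SAEs after new anticancer therapy is already a separate paragraph and stays as it is.
2. In the same edit, reconcile the stop at new anticancer therapy in Sections 6.1.1 and 6.2.1 with Sections 5.3 and 8.3.1. Either state the cut-off in the endpoint definition or remove it from the collection rules.
3. Send sites a short clarification, and check which window the case report form and its completion guidelines use.
4. Query Days 101 to 135 only where a site or form is found to have applied 100 days.

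The cost is a small text change, one letter and a limited query effort. Reported SAE counts may rise slightly. No change to design or sample size is needed.

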6.2 Non-serious Adverse Events

A *non-serious adverse event* is an AE not classified as serious.

6.2.1 Non-serious Adverse Event Collection and Reporting

The collection of non-serious AE information should begin at initiation of study drug and for 135 days after discontinuation of dosing or until starting a new anti-neoplastic treatment (whichever occurs first). Non-serious AE information should also be collected from the start of a placebo lead-in period or other observational period intended to establish a baseline status for the subjects.

Non-serious AEs should be followed to resolution or stabilization, or reported as SAEs if they become serious (see [Section 6.1.1](#)). Follow-up is also required for non-serious AEs that cause interruption or discontinuation of study drug and for those present at the end of study treatment as appropriate. All identified non-serious AEs must be recorded and described on the non-serious AE page of the CRF (paper or electronic).

Completion of supplemental CRFs may be requested for AEs and/or laboratory abnormalities that are reported/identified during the course of the study.

Immune-mediated adverse events are AEs consistent with an immune-mediated mechanism or immune-mediated component for which non-inflammatory etiologies (eg, infection or tumor progression) have been ruled out. IMAEs can include events with an alternate etiology which were

exacerbated by the induction of autoimmunity. Information supporting the assessment will be collected on the subject's case report form.

